8.6.1 Obtaining Data Files

Not applicable

8.6.2 Review and Verification of Data Quality

The accuracy, data quality, and internal consistency of the data from this study will be verified. Data curation is responsible for the accuracy, quality, completeness, and internal consistency of the data from this study. Data handling, including data quality assurance, will comply with applicable international regulatory guidelines. Data curation and control processes specific to this study, along with all steps and actions taken regarding data curation and data quality assurance, will be confirmed in data curation plan.

Standard operating procedures will be used to guide the conduct of the study. These procedures include internal quality audits of the data, accuracy and consistency of extracted data, validation of coding, rules for secure and confidential data storage, methods to maintain and archive documents, quality country procedure for

Protocol Number: 20240175

Date: 27 March 2025 Page 29 of 47

programming, standards for writing analysis plans, and requirement for senior scientific review.

eCRFs received will be processed and reviewed for completeness, consistency, and the presence of mandatory values. Applicable terms will be coded according to the coding conventions for this study. Logical checks will be implemented to ensure data quality and accuracy. The eCRF will give immediate feedback if data are missing, out of range, illogical or potentially erroneous. To avoid systematic mistakes when entering data, each site will be asked to document data of 2 patients in the eCRF. Subsequently, the data entry will be checked for consistency and logic. Possible inconsistencies will be discussed and resolved with the site before additional patients are documented by the respective site.

Data will be verified using the data source by the study monitor and reviewed for consistency by data curation using both automated logical checks and manual review. All data extracted will be approved by the investigator at the investigational center. This approval acknowledges the investigator's review and acceptance of the data as being complete and accurate.

Data extraction at each site will be monitored both remotely and in an on-site manner. Written programming will be reviewed independently. The secure storage of data, study programs, log files, output files and back up will be ensured as required by regulatory guidelines. All key study documents, such as the statistical plan and study reports, will undergo quality control and review.

8.7 Data Analysis

8.7.1 Planned Analyses

The analyses of all objectives will be performed using descriptive statistical methods. No hypotheses testing is planned.

8.7.1.1 Interim Analysis/Analyses

The interim analyses will be conducted after completing the data extraction of 30 patients in BOAO Pilot Zone, including analyses to:

- Characterize the safety profile of sotorasib in Chinese patients.
- Describe real-world OS CC

CCI

Protocol Number: 20240175

Date: 27 March 2025 Page 30 of 47

8.7.1.2 Primary Analysis

The primary analyses will be conducted after completing data extractions of all patients from BOAO Pilot Zone and Hong Kong SAR, to:

• Characterize the safety profile of sotorasib in Chinese patients.

8.7.2 Planned Method of Analysis

8.7.2.1 General Considerations

All data analyses will be performed using appropriate software such as SAS statistics software version 9.3 or higher (SAS Institute Inc., Cary, NC). An analysis plan with a detailed description of analyses to be performed will be developed.

All analysis will be conducted separately for patients in BOAO Pilot Zone and Hong Kong SAR CDARS.

8.7.2.2 Missing or Incomplete Data and Lost to Follow-up

This is a retrospective chart review study. Information which is not included in the patient medical charts cannot be reported. Missing data will not be replaced by imputation methods. All analyses will be conducted in patients with available information.

As described in Section 8.4, during the treatment period, physicians proactively follow up with patients in BOAO Pilot Zone. In addition, as advanced NSCLC is a life-threating disease which needs close support from physicians specialized in treating NSCLC, it is expected that patients remain at same site for treatment.

Outcome assessment up to the end of follow-up defined in Section 8.2.6 will be included in the analysis.

8.7.2.3 Descriptive Analysis

8.7.2.3.1 Description of Study Enrollment

Patients will be selected by reviewing the medical charts and enrolling those who meet the eligibility criteria and sign ICF, if required.

8.7.2.3.2 Description of Patient Characteristics

Patients who are 18 years of age or older, have KRAS p.G12C-mutated locally advanced or metastatic NSCLC, previously treated with at least 1 prior systemic therapy

Protocol Number: 20240175

Date: 27 March 2025 **Page 31 of 47**

and have been treated with at least 1 dose of sotorasib in clinical practice will be included in the study.

8.7.2.4 Analysis of the Primary, Secondary, and Exploratory Endpoint(s)

Frequencies will be presented for categorical demographic (eg, sex, smoking status), clinical (eg, prior treatments, tumor mutations), and pathological (eg, stage, histology) variables. Descriptive statistics (mean, median, standard deviation, and range) will be presented for continuous variables.

The proportion of AEs will be summarized by count and proportions, specifically the proportion of patients experiencing AEs relative to the total number of patients.

Median OS and PFS and the corresponding 95% confidence intervals (CIs) will be calculated using Kaplan-Meier estimates. The estimated survival probabilities, along with corresponding 95% CIs using Kaplan-Meier method will be presented for patients at 6 and 12 months.

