- Last treatment with sotorasib + 30 days

As the Hong Kong SAR CDARS database is a closed-loop database with linkage to the regional deaths registry, patients without evidence of death in the CDARS database by the data cut-off date were considered alive, and their last activity date will be the same as the cut-off date.

For objective of OS, follow-up per patient will continue through earliest date of last clinical activity in the data source, data cut-off in the data source, or death.

Variables

Outcomes:

- Primary: The patient incidence of AEs after sotorasib initiation.
- Secondary: OS from clinician notes in electronic health record and linkage to mortality records (where available).
- Exploratory: CCI

 CCI

Exposure:

o Use of sotorasib

Protocol Number: 20240175

Date: 27 March 2025 **Page 14 of 47**

Covariates

Key demographic, clinical characteristics, and pathology covariates including and not limited to age, sex, smoking status, body mass index (BMI), Eastern Cooperative Oncology Group (ECOG) performance status, histology, tumor stage, programmed death-ligand 1 (PD-L1) protein expression, presence of tumor mutations or rearrangements, laboratory test, electrocardiogram (ECG) and radiology, prior systemic treatments, brain metastases (if information available), prior lines of systemic therapy, and concomitant medications.

Study Sample Size

By the time of data cut-off, an estimated about 100 and 15 patients will have been treated with sotorasib and eligible for study inclusion from BOAO Pilot Zone and Hong Kong SAR, respectively. For a sample size of 115 patients and the observation of a proportion of 50% patients with an endpoint the largest level of margin of error (indicating the lowest level of precision) is \pm 9.14%.

Data Analysis

Frequencies will be presented for categorical demographic, clinical, and pathological variables. Descriptive statistics (mean, median, standard deviation, and range) will be presented for continuous variables.

The patient incidence of AEs will be summarized by count and proportions, specifically the proportion of patients experiencing AEs relative to the total number of patients. Median OS and PFS, along with the corresponding 95% confidence intervals (CIs) will be calculated using Kaplan-Meier estimates. The estimated survival probabilities, along with the corresponding 95% CIs will be presented for patients at 6 and 12 months.

CC

5. Amendments and Updates

None

6. Rationale and Background

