The electronic health record database in BOAO Pilot Zone participating hospitals contain critical data relevant to the research question, for example the exposure of sotorasib, AEs, effectiveness outcomes, and key covariates. The electronic medical record (EMR) system in Hong Kong SAR contains both structured data, including demographic information, diagnosis, prescription records, procedure, hospital stay, discharge information, and unstructured data, including genetic testing results, radiographical and imaging exam results and additional patient information. Critical variables are covered and will be extracted to the extent possible.

Accuracy of the definition of exposure, outcomes, and covariates

Eligible patients need to be physically at BOAO Pilot Zone hospitals to receive treatments, enabling complete sotorasib exposure assessment in electronic health record databases. In addition, as advanced NSCLC is a life-threating disease which

Protocol Number: 20240175

Date: 27 March 2025 **Page 18 of 47**

needs close support from physicians specialized in treating NSCLC, it is expected that patients remain at same site in BOAO Pilot Zone for treatment. As sotorasib is used through the pre-registration program, local government authorities require close monitoring and reporting of safety events which were well documented in hospitals by physicians. Besides, physicians were reported to proactively follow-up with patients and document patients' treatment information, follow-up evaluations (both within and outside BOAO Pilot Zone), safety events, treatment outcome and discontinuation in hospital electronic health record database. These real-time data sources will be used to extract comprehensive and accurate outcome and key covariates.

Data will be verified using the data source by the study monitor and reviewed for consistency. All data extracted will be approved by the investigator at the investigational center. Adverse event grades and relationship to sotorasib may be unavailable or unconfirmable for some patients due to limitations in the available information. The level of missingness will be described and results related with grade will be interpreted with caution.

Sample size

The feasibility check indicates that at the data cut-off, approximately 100 sotorasib treated patients in BOAO Pilot Zone, and about 15 patients in Hong Kong SAR, will be eligible for inclusion. Details of sample size calculation are provided in Section 8.5.

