8.7.3 Analysis of Safety Endpoints

All patients participating in the study who meet the eligibility criteria will be included in the safety analysis. All AEs will be coded using MedDRA. For safety outcomes defined in Section 8.3.2, count and proportions will be calculated, respectively.

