8.9.4 Limitations Due to Missing Data and/or Incomplete Data

A limitation of retrospective chart review studies is that only data documented in patient medical records can be transmitted in the eCRF.

We expect that most patients with NSCLC remain at the BOAO Pilot Zone, or same site in Hong Kong SAR for the entire treatment of the disease. To meet the objectives of this study, data will be abstracted which in general are documented in the patient medical records in routine oncology care except for AE grade. Adverse events grade and relationship to sotorasib may not be available for some patients or unable to be confirmed based on the available information. Adverse events grades and relationship to sotorasib will be extracted to the extent possible. Additionally, information on deaths may be incomplete, as the analysis will only use reported deaths. Missingness and incomplete data on the covariates, and potentially others not listed here, may limit the ability to assess certain subgroup of interest. The level of missingness will be described and no attempts at imputation will be made in this study.

Since sotorasib is not widely available in mainland China, the early adopters included in this study may not be fully representative of the broader population that will eventually receive this treatment. For example, as patients are required to travel to BOAO Pilot Zone for therapy, they may generally be healthier than the average patient. Despite this limitation, this study will still provide valuable insights into the safety and effectiveness profile of sotorasib in a real-world context.

During the data abstraction period, manual queries or source data verification will be done. Additionally, missing information in mandatory variables or inconsistent data on these variables in the eCRF will be flagged directly in the eCRF so that it can be added or corrected immediately while entering the data. Furthermore, the monitor will conduct calls with the sites and/or send e-mails to establish progress, address any challenges, and refresh investigators on study responsibilities. In addition to a planned proactive outreach, the data curation will continue to manage investigator-initiated study-related enquiries as needed.

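### Sections 8.7.2.2 and 8.7.2.4 set different denominators for AE incidence, and over all patients without imputation, unclassifiable events lower six of the eight primary safety endpoints

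*Protocol*

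**What the plan says.** Three places put AE incidence over everyone. The abstract (Section 4, Data Analysis) and Section 8.7.2.4 both use the wording "specifically the proportion of patients experiencing AEs relative to the total number of patients". Section 8.7.3 adds: "All patients participating in the study who meet the eligibility criteria will be included in the safety analysis".

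Section 8.7.2.2 reads differently. It states "Missing data will not be replaced by imputation methods" and then "All analyses will be conducted in patients with available information". It makes no exception for safety.

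The protocol expects gaps in the two items that classify an AE. Section 6.3: "Adverse event grades and relationship to sotorasib may be unavailable or unconfirmable for some patients due to limitations in the available information". Section 8.9.4: "Adverse events grade and relationship to sotorasib may not be available for some patients or unable to be confirmed based on the available information". The planned response is to describe the missingness. Section 6.3 adds a caution, but only for results that depend on grade.

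Section 8.3.2 lists eight primary safety endpoints. Six are treatment-related categories: any, grade 3 or worse, serious, leading to discontinuation, leading to dose reduction, and leading to death. The other two (TEAEs and AEs of interest) need neither relationship nor grade. Hong Kong records only AEs of interest, and Section 8.7.2.1 analyses the two regions separately, so the six relationship-based endpoints rest on BOAO alone.

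**The concern.** The text gives two answers to one question: who is in the denominator when a patient had an AE but the chart does not settle whether it was related, or how severe it was? The two answers give different percentages from the same data. Section 6.3 says BOAO patient-level data will be submitted so that a regulator can reproduce the results, which requires a single rule.

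Under the all-patient rule the error has a direction. Without imputation, an event of unknown relationship cannot enter a treatment-related numerator, yet the patient stays in the denominator. A truly related event that cannot be classified is then reported as no event, and the rate can only fall. This touches most of the primary objective. Describing how much is missing does not show a reader how far each rate could move. Relationship, which drives all six endpoints, does not even receive the caution given to grade.

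**Working it through.** **The plan's own figure.** Section 8.5 uses e = 1.96 × √(p(1−p)/n). At p = 50% and n = 115 this gives 9.14%, as printed, and the other four rows of Table 1 also reproduce (8.95, 8.38, 7.31, 5.48%). For the six BOAO-only endpoints n is about 100, so the largest margin is 9.80%.

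**Inputs.**
- n = 100 for BOAO (Sections 6.3 and 8.5).
- Illustrative true incidences from Section 6.2: 69.8% for any treatment-related AE (phase II), 33% for grade 3 or worse (phase III) and 11% for serious treatment-related AEs (phase III). Section 6.2 does not repeat the words treatment-related beside the 33%, so it serves only as an illustration.
- m = share of patients with a truly qualifying event whose qualifying events are all unclassifiable. The protocol gives no value; 10%, 20% and 30% are assumptions.

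**All-patient denominator, no imputation.** Reported incidence = p(1−m); shortfall = m × p.

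| True p | m = 10% | m = 20% | m = 30% |
|---|---|---|---|
| 69.8% | 62.8% | 55.8% | 48.9% |
| 33% | 29.7% | 26.4% | 23.1% |
| 11% | 9.9% | 8.8% | 7.7% |

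At m = 20% the shortfall for p = 69.8% is 14.0 points, against a margin of error of 9.0 points at n = 100. For p = 33% it is 6.6 points against 9.2.

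**Available-information denominator.** Unclassifiable patients leave both numerator and denominator, while AE-free patients have nothing to be missing and stay. Let a be the share of patients with any AE, and k the share unclassifiable among AE patients with no truly qualifying event. Then

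reported incidence = p(1−m) / [1 − m·p − k(a−p)].

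For p = 33%:
- m = 20%, k = 0 (only truly qualifying patients are unclassifiable): 26.4/93.4 = 28.3%.
- a = 90%, m = k = 20%: 26.4/(100 − 6.6 − 11.4) = 26.4/82 = 32.2%.
- a = 90%, m = 10%, k = 30%: 29.7/(100 − 3.3 − 17.1) = 29.7/79.6 = 37.3%.

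The rate is overstated when k(a−p) > m(1−p). With a = 90% and p = 33% that means k > (0.67/0.57)m, or about 1.18m. The values of a and k are assumptions too.

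**Both rules on one data set.** Suppose 26 of 100 patients have a classified qualifying event and 20 others have only unclassifiable candidates. Over all patients: 26/100 = 26.0%. Over patients with available information: 26/80 = 32.5%. Bounds: 26/100 to (26+20)/100, or 26% to 46%.

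**The case against.** The best reply is that there is no real conflict. Sections 4, 8.7.2.4 and 8.7.3 are specific to AEs and 8.7.2.2 is general, so the specific rule governs. That is a reasonable reading, but the protocol does not state it, and 8.7.2.2 says it applies to all analyses. Choosing this reading also selects the denominator whose error is one-sided.

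A second reply is that tabulation of AEs with missing attributes belongs in the SAP. In part that is right: no section says such events are coded as non-events, and an unknown row would fit the promise to describe missingness. But the headline treatment-related rate still excludes those events, and the no-imputation rule in 8.7.2.2 and 8.9.4 leaves the SAP no clear authority to show them as related, even as a bound.

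A reader might infer that both denominators understate incidence. The documents do not support that. It holds under the available-information rule only if the unclassifiable patients are mainly those with truly qualifying events; once enough non-qualifying AE patients also drop out, the rate is overstated, as the 37.3% case shows.

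Other points stand. The protocol describes mandatory safety reporting in BOAO and verification of grade by investigators, so missingness may be small. A patient with another classified qualifying event still counts. TEAEs and AEs of interest provide a safety picture that needs no attribution. Making missing-equals-related the sole main analysis would exchange possible understatement for possible overstatement.

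**Conclusion.** The point holds in this form. The denominator is stated in two ways, missing relationship and grade are expected, and six of the eight primary endpoints depend on relationship. Under the all-patient rule without imputation, incidence is understated by m × p. For m between 10% and 30% that is 7.0 to 20.9 points at p = 69.8%, 3.3 to 9.9 points at p = 33%, and 1.1 to 3.3 points at p = 11%. Under the available-information rule the direction is not fixed.

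The size in this study is unknown: every value of m, a and k is assumed, and the true incidences are borrowed from other trials. It would be wrong to conclude that the reported rates will be materially too low. What can be said is that, as written, they could be, and that the planned tables need not show by how much.

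**What to change.** 1. In Section 8.7.2.2, state that the available-information sentence does not change the AE denominator, which is all eligible BOAO patients for the six treatment-related endpoints.
2. For each of these endpoints, report the number of patients whose only candidate events are unclassifiable, separating missing relationship from missing grade where both apply.
3. Give a lower bound (unclassifiable = non-event) and an upper bound (unclassifiable = event), and state that these bounds are exempt from the no-imputation rule in Sections 8.7.2.2 and 8.9.4.
4. Add all-causality rows for grade 3 or worse, serious, and AEs leading to discontinuation, dose reduction or death. These need no attribution and use data already being extracted; the grade 3 or worse row still needs bounds for missing grade.

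The cost is a short protocol clarification, a matching SAP rule and extra table rows. The downside is that upper-bound rates will look less favourable, by an amount that depends on how much is missing.

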6.3 Feasibility (fit-for-purpose evaluation)

Active and accessible data:

As introduced in Section 6.2, sotorasib became available in BOAO Pilot Zone in August 2021 through a pre-registration program. Sotorasib will be continuously available at BOAO Pilot Zone before data cut-off (~Q2 2025). BOAO Pilot Zone is the only place in mainland China with sotorasib access and thus enable a complete capture of all mainland Chinese patients treated with sotorasib in real-world and clinical settings.

Protocol Number: 20240175

Date: 27 March 2025 Page 17 of 47

Patient-level data in BOAO Pilot Zone will be available and submitted to enable a regulatory authority to reproduce the results.

The Hong Kong SAR Clinical Data Analysis and Reporting System (CDARS) database will be used to extract patients treated with sotorasib in Hong Kong SAR. Clinical Data Analysis and Reporting System is a population-based database with medical records covering residents in Hong Kong SAR who received care from any public hospital. It also contains data on causes of death through its internal linkage to regional deaths registry and have been used in various disease area including lung cancer (Philip et al, 2024). Academic researchers in Hong Kong SAR will be able to apply and access the database. The database is used for efficiency; however, the information is drawn from detailed patient records, ensuring that the analysis is based on comprehensive and accurate medical chart data. Details of data sources are provided in Section 8.4.

Ethical and security requirements

The study will follow requirements of the governance and sites. All data extracted will be anonymized. The study protocol will be reviewed by the IRB of each site in BOAO Pilot Zone and Hong Kong University in Hong Kong SAR. In addition to governance and the IRB, the study will comply with Amgen's global standard operation procedures and technical governance for observational research. The International collaboration Human Genetics Resources Administration of China application will be submitted for BOAO Pilot Zone. Details are provided in Section 9.

Coverage of critical variables

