8.2.1 Study Period

The study eligibility period extends from the patients' index date (ie, the initiation of sotorasib) to the end of study period, defined as the earliest occurrence of patient's last activity date in the data source, data cut-off date or death.

The first available sotorasib use in BOAO Pilot Zone is around August 2021 through a pre-registration program. Specifically, sotorasib was included in the following hospitals'

Protocol Number: 20240175

Date: 27 March 2025 **Page 20 of 47**

drug lists and available for prescription: Ruijin Hainan Hospital in July 2022; BOAO Super Hospital in August 2021; BOAO Hengda Hospital in November 2021; and BOAO future Hospital in January 2022. The data cut-off will be the EC submission date (~ Q2 2025).

Sotorasib was approved in Hong Kong on April 29, 2022. The eligible treatment should occur after April 29, 2022. The data cut-off will be the date of data extraction (~ Q3 2025).

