8.2.3.1 Inclusion Criteria

- Adult (≥ 18 years) as of the index date
- KRAS p.G12C-mutated locally advanced or metastatic NSCLC
- Received at least 1 dose of sotorasib
- Receipt of at least 1 prior systemic therapy before use of sotorasib
- · Obtained ICF, if required

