8.9.3 Analysis Limitations

CCI
We will perform a sensitivity analysis in which patients who
switch to other commercially available drugs or clinical trial medications will be censored
for sotorasib treatment.
Estimates of OS are likely to be immature in this study due to the potentially short
observation period for some patients. Patients without evidence of death by the data
cut-off will be censored at their last confirmed activity date, potentially underestimating
the true time at risk. A sensitivity analysis will follow these patients to the end of the
study instead of censoring them at their last confirmed activity date.
CCI

Protocol Number: 20240175

Date: 27 March 2025 Page 35 of 47

No further analysis limitations are expected.

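### The primary AE endpoint is summarised only as a crude proportion over all patients, although data cut-off or last activity can cut the safety window short; add a fixed-time cumulative incidence beside it

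*Protocol*

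**What the plan says.** Section 8.7.2.4 summarises AEs by count and proportion, "specifically the proportion of patients experiencing AEs relative to the total number of patients". Section 8.7.3 sets the denominator, "All patients participating in the study who meet the eligibility criteria will be included in the safety analysis", and the statistic: "For safety outcomes defined in Section 8.3.2, count and proportions will be calculated, respectively". The abstract (section 4, Data Analysis) says the same.

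Inclusion asks only for minimal exposure, "Received at least 1 dose of sotorasib" (8.2.3.1). No interval between index date and cut-off is required. Entry in BOAO is long and open-ended: "The first available sotorasib use in BOAO Pilot Zone is around August 2021 through a pre-registration program" (8.2.1), and "Sotorasib will be continuously available at BOAO Pilot Zone before data cut-off" (6.3), which is about Q2 2025. Hong Kong entry runs from after 29 April 2022 to about Q3 2025.

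The abstract's Follow-up paragraph ends safety follow-up at the earliest of last clinical activity, data cut-off, death, or "Last treatment with sotorasib + 30 days".

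Short observation is acknowledged for overall survival: "Estimates of OS are likely to be immature in this study due to the potentially short" observation period of some patients (8.9.3). OS is analysed by Kaplan-Meier with censoring. Section 8.9 names no matching limitation for AEs.

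**The concern.** A patient who starts a few weeks before the cut-off, or whose record stops while still on drug, stays in the denominator for the whole safety window but can contribute events only from the observed part. Unobserved time can only remove events from the numerator. As an estimate of incidence over treatment plus 30 days, the crude proportion can therefore err only downward, which for a safety objective is the unfavourable direction.

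The plan also builds in one comparison with unequal follow-up. Table 2 (8.7.2.5.1) lists initiation before versus on or after 1 January 2023. Nearly all windows cut by the data cut-off belong to the later group. If AEs are tabulated by this factor, safety could appear to improve over calendar time with no change in risk.

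**Working it through.** **The plan's own figure.** Table 1 uses e = 1.96 × √(p(1−p)/n). At n = 115, p = 30%: 1.96 × √(0.30 × 0.70/115) = 8.38 points, as printed. The other four rows also reproduce (9.14, 8.95, 7.31, 5.48). Section 8.7.2.1 analyses the regions separately, so the relevant margins at 30% are 8.98 points (BOAO, n = 100) and 23.19 points (Hong Kong, n = 15).

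**Inputs from the protocol.** Entry window about 44 to 46 months in BOAO and about 40 in Hong Kong (8.2.1). Median PFS 5.6 months (sections 4 and 6.2), used as a proxy for treatment duration. Illustrative incidence 33%, the grade 3 or worse figure in 6.2.

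**Assumptions, not in the protocol.** Exponential treatment duration, the distribution of entry dates, and AE onset. Loss to follow-up before cut-off is not modelled.

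**Windows cut short.** Mean duration is 5.6/ln 2 = 8.08 months, and the window is W = duration + 1 month. With uniform entry over A months,

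P(cut) = E[min(W, A)]/A = (1 + 8.08 − 8.08·e^(−(A−1)/8.08))/A.

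A = 46 gives 19.7% and A = 44 gives 20.5%. The share with under 3 months from first dose to cut-off is 3/46 = 6.5% or 3/44 = 6.8%.

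**Incidence seen.** With C the time from first dose to cut-off and T the time to first AE, the crude proportion estimates P(T ≤ min(W, C)), while the full-window value is P(T ≤ W). Each model is calibrated so that P(T ≤ W) = 33%.
- Early-onset model: a susceptible fraction (0.36, 0.41 or 0.52) has exponential onset with mean 1.5, 3 or 6 months.
- Hazard model: everyone is at risk, with Weibull shape 0.5, 0.7 or 1 (shape 1 is constant hazard). For shape 1, solving 1 − e^(−h) × 0.1238/(0.1238 + h) = 0.33 gives h = 0.052 per month.

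| Entry pattern | Model | Windows cut | 33% is seen as |
|---|---|---|---|
| BOAO, uniform, 46 months | onset 1.5 / 3 / 6 | 20% | 32.1 / 31.4 / 30.5% |
| BOAO, uniform, 44 months | shape 0.5 / 0.7 / 1 | 20.5% | 30.5 / 29.7 / 28.7% |
| BOAO, rising to cut-off, 46 months | onset 1.5 / 3 / 6 | 33% | 31.2 / 29.9 / 28.4% |
| BOAO, falling, 46 months | onset 1.5 / 3 / 6 | 7% | 33.0 / 32.9 / 32.6% |
| Hong Kong, uniform, 40 months | onset 1.5 / 3 / 6 | 22.5% | 31.9 / 31.1 / 30.1% |
| Hong Kong, rising, 40 months | onset 1.5 / 3 / 6 | 36% | 30.9 / 29.5 / 27.8% |

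**Calendar subgroup.** Uniform entry over 44 months, with 1 January 2023 falling 17 months in. At an identical full-window risk of 33%, the earlier group shows about 33%. The later group shows 26.0% (shape 1) to 29.0% (shape 0.5), or about 29% to 31% in the early-onset model.

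**The case against.** The strongest reply is that nothing stated is an error. The study is descriptive, the endpoint is patient incidence, and patients with an event over all treated patients is the conventional summary of AEs during observed exposure. The protocol says openly that follow-up ends at the earliest of four dates. This stands, and it is why the crude proportion should be kept.

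A second reply is that further summaries belong in the SAP, which 8.7.2.1 promises and which is not at hand. This stands in part: the SAP may add them. But the protocol itself names counts and proportions as the safety summary and recognises short observation only for OS.

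A third is that loss while on drug is limited. BOAO patients must return to continue therapy and physicians follow them proactively. Hong Kong patients without a recorded death have last activity set to the cut-off. This stands, but it does nothing about truncation by the cut-off itself. Nor does the Table 1 margin answer it: that margin is sampling error, and the shift is systematic and adds to it.

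Two stronger readings are tempting. A reader might infer that the trial percentages in 6.2 come from fully followed cohorts, so that any comparison with them is biased. The protocol does not describe AE follow-up in those trials, so this is unsupported. A reader might also take the shift to be about 7 points. Uniform entry gets there (33% seen as 26.1%) only with a constant hazard plus a 2% monthly loss to follow-up, and no figure in the protocol supports that loss.

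**Conclusion.** The point holds as a limit on what the crude proportion can be used for, not as a fault in the proportion itself. It is biased downward relative to incidence over treatment plus 30 days, and it is not comparable across groups with different follow-up. Follow-up ended by death or by treatment end plus 30 days is not truncation and contributes nothing to this bias.

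Under uniform entry the shift at 33% is roughly 1 to 4 points. In the early-onset model it is near zero if entry was concentrated early and about 5 points if it was concentrated late. These are single-departure scenarios. Stacking unfavourable assumptions, such as constant hazard with late-weighted entry, would go further, but the protocol gives no entry dates, onset times or loss rates to justify quoting that as an upper end. The shift is smaller than the sampling margin in either region. The calendar-period subgroup is the more exposed use, with an artificial difference of about 2 to 7 points under uniform entry at equal true risk. This should be changed, but it does not invalidate the primary analysis.

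**What to change.** 1. Keep the crude count and proportion.
2. Add to 8.7.2.4 and 8.7.3 the cumulative incidence of first AE at 3 and 6 months for the listed AE categories, by the Aalen-Johansen method. Censor at data cut-off or last activity, and treat death and end of treatment plus 30 days as competing events. One minus Kaplan-Meier, censoring at death, would overstate incidence.
3. Use that estimate for any AE comparison by calendar period of initiation.
4. Report the distribution of safety follow-up time beside the crude proportions. Exposure-adjusted rates are an optional supplement; a single rate is mainly interpretable when the hazard is roughly constant.
5. State in 8.9.3 that short observation affects AEs as well as OS.

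Restricting the crude proportion to patients with at least 3 months before cut-off is not a substitute. It drops about 7% of patients while about 20% of windows are cut, and in the hazard model 33% is still seen as 30.3% to 31.6%.

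The cost is wording and a few table rows. Treatment dates are already extracted (8.3.1), and AE onset dates are needed to classify events as treatment-emergent. Intervals in Hong Kong, with about 15 patients, will be wide.
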